#### *iGO-PK Model*

This method was developed using data generated from a previous ATX single-dose PK study conducted at Children's Mercy Hospital (Brown et al., 2016). This model stratifies participants into two distinct populations: individuals who are CYP2D6 PM and those who non-PMs, i.e. IM, EM1, EM2, and UM (read above for more details on *CYP2D6* genotype and phenotype prediction). With the new changes to *CYP2D6* genotype-to-

phenotype interpretation and study design, the only major change is that children with two reduced function alleles will be modeled as an IM. Analysis of the previous PK study found that in non-PM participants, the dose-exposure relationship was best described using a two-compartment model with first order absorption and first order clearance. In PM participants, dose-exposure was best described using a one compartment model with first order absorption, first order clearance, and a secondary peaking component. Additionally, lean body weight (LBW) and obesity status (positive or negative) variables were found to significantly impact variability in ATX exposure in both models.

Retrograde extrapolation of an initial dose of ATX for PK Study 1 will be determined by setting the desired  $C_{max}$  goal at steady-state ( $C_{max,ss}$ ) to 400 ng/mL, and incorporating patient specific parameters CYP2D6 AS, LBW, and obesity status. The actual dose dispensed will be as close as possible to the model generated dose, given the available atomoxetine capsule formulations. Additionally, we will also consider the most convenient combination of capsules for a child to take and how a prescriber would dose this medication in a naturalistic setting. During the course of the study, we will also be monitoring clinical response and toxicity. The exposure ( $C_{max,ss}$ ) may be titrated down to below 400 ng/mL to reduce toxicity or up to 800 ng/mL to increase response as tolerated.

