  - i. These tests may be omitted if these data were collected in the week prior, at the discretion of the study coordinator, the physician performing the physical exam, or any person designated in the delegation of authority log.
- g. Collect urine for urinalysis with microbiology.
- h. Perform urinary pregnancy test on female subjects.
- i. Collect baseline urine sample (~10 mL) for predose urine sample and CYP2D6 biomarker analysis.
- j. Confirm prior to dosing that participant is:
  - i. Healthy enough to continue Research Visit 2 (sign off on safety labs and physical exam sheet by physician).
  - ii. Not pregnant, females only (urine pregnancy test).
- k. Place two sweat patches on the participants back. The sweat patch is 15.4 cm^2 in size and consists of a cellulose blotter paper collection pad

(PharmChek®, PharmaChem Laboratories, Menlo Park, CA). Prior to patch placement, clean the area of skin to which the patch will be applied with rubbing alcohol.

- i. Collect pre-dose blood, blood pressure, and heart rate prior to dosing medication.
- m. Administer dose of atomoxetine according to prescription.
- n. Collect 3 mL of blood, blood pressure, and heart rate at the following time points after dose administration:
  - i. Timeframe:
    - i. Study Design 1: 0.5, 0.75, 1, 1.5, 2, 3, 4, 6, 8, 10, 12, 16, 20, 24, 48, and 72 hours.
    - ii. Study Design 2: 0.5, 0.75, 1, 1.5, 2, 3, 4, 6, 8, 10, and 12 hours.
    - iii. A window of  $\pm$  5 minutes is acceptable for blood draws at time points 0.5 – 2 hours.
    - iv. A window of  $\pm$  15 minutes is acceptable for blood draws at all other time points.
  - ii. Collection Instructions: 2 mL of blood will be collected in a EDTA tube and 1 mL of blood will be collected in a serum gel separator tube.
  - iii. Processing: Within an hour of collecting sample, plasma and serum will be separated by centrifugation at 4°C (1000 – 2000 g x 10 min), aspirated manually, and transferred to polypropylene cryovials for storage at -70°C until analysis.
- o. Collect and pool urine starting after dose administration.

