#### Pharmacokinetics:

Estimation of the pharmacokinetic parameters and generation of the statistical analyses on the PK parameters will be performed by The Division of Clinical Pharmacology Toxicology & Therapeutic Innovation at the Children's Mercy Hospital, Kansas City, MO. Pharmacokinetic analyses will be conducted using Kinetica™ version 5.0 (ThermeElectron, Philadelphia, PA). Plasma ATX concentration versus time data will be curve fit using a peeling algorithm to generate initial polyexponential parameter estimates. Final parameter estimates will be determined from an iterative, nonlinear weighted least squares regression algorithm with reciprocal ( $1/y^2_{\text{calc}}$ ) weighting. Model-dependent pharmacokinetic parameters will be calculated from final polyexponential parameter estimates. Final model selection will be performed by evaluating the

goodness-of-fit criteria including; the objective function, Akaike & Schwartz criteria, standard deviations and coefficients of variation for the polyexponential parameters estimates and the correlation matrix detailing the degree of interdependence between the parameter estimates for each model. In the event that an insufficient number of post-peak ATX plasma concentration time points are available, a model-independent approach will be used and parameters of interest calculated using standard techniques. Specifically,  $C_{max}$  and  $T_{max}$  will be obtained by direct examination of the plasma concentration versus time profile. The area under the plasma concentration versus time curve during the sampling period ( $AUC_{0-n}$ ) will be calculated using the mixed log-linear rule and extrapolation of the AUC to infinity ( $AUC_{0-\infty}$ ) calculated by summation of  $AUC_{0-n} + Cp_n/\lambda_z$ , where  $Cp_n$  represents the final plasma concentration predicted from the fitted apparent terminal elimination phase and  $\lambda_z$  is the apparent terminal elimination rate constant. Model-independent pharmacokinetic parameters will then be calculated using standard (i.e., statistical moment theory) techniques. ATX metabolites *N*-desmethylatomoxetine (NDM-ATX), 4-hydroxyatomoxetine (4-OH-ATX) and hydroxyl-2-carboxylatomoxetine (OH-2-COOH-ATX) pharmacokinetics will be evaluated in a fashion analogous to that described for the parent compound.

The following PK parameters will be derived by non-compartmental analysis from plasma concentration data following a single dose study drug administration:

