$C_{max}$	Peak plasma concentration determined from the observed data
$T_{max}$	Time to observed maximum drug concentration
$AUC_{0-\tau}$	Area under the plasma concentration versus time curve, determined by log-linear trapezoidal estimation, to the 12 or 24 hour time point (depending on CYP2D6 AS designated study design).
$AUC_{0-\infty}$	Area under the concentration versus time curve to infinity, determined by log-linear trapezoidal estimation $AUC_{0-\tau} + C_{\tau}/k$ Where $k$ is the elimination rate constant defined as the negative slope following maximum concentration determined by least squares regression from terminal phase data.
$T_{1/2}$	Terminal half-life determined by quotient $0.693/k$
$CL/F$	Oral clearance determined by quotient dose/ $AUC_{0-\infty}$
$Vd/F$	Terminal phase volume of distribution determined by Dose/ $k \cdot AUC_{0-\infty}$

fm	Fraction of drug metabolized through different pathways of biotransformation
----	--

The following PK parameters will be derived by non-compartmental analysis from plasma concentration data following chronic dosing to steady-state of study drug:

$C_{max,ss}$	Peak plasma concentration determined from the observed data at steady-state
$T_{max, ss}$	Time to observed maximum drug concentration at steady-state
$AUC_{0-\tau,ss}$	Area under the plasma concentration versus time curve, determined by log-linear trapezoidal estimation, to the 12 or 24 hour time point (depending on CYP2D6 AS designated study design).
$T_{1/2}$	Terminal half-life determined by quotient $0.693/k$
$CL/F_{ss}$	Oral clearance determined by quotient dose/ $AUC_{0-\infty}$
$Vd/F_{ss}$	Terminal phase volume of distribution determined by Dose/ $k \cdot AUC_{0-\infty}$

iGO-PK Model Update: The current iGO-PK Model (Version 1.0) uses ATX pharmacokinetic data from 24 pediatric participants (Brown et al., 2016). Since the building of Version 1.0, more ATX pharmacokinetic data has been collected from studies conducted at Children's Mercy Hospital (IRB# 16010069) and this current study. The data will be used to update and refine the iGO-PK model when it has been determined that sufficient new data has been collected. This determination will be made by the Principal Investigators and other Co-Investigators.

Pharmacodynamics:

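### Section 20.1 gives two conflicting rules for single-dose AUC0-∞ in Study Design 1, and the one in the parameter table leaves out the observed 24–72 h area

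*Combined protocol and SAP*

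**What the plan says.** Section 20.1, Pharmacokinetics, describes single-dose AUC0-∞ twice.

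- **Parameter table (single dose).** AUC0-τ is "determined by log-linear trapezoidal estimation, to the 12 or 24 hour time point (depending on CYP2D6 AS designated study design". The next row is "Area under the concentration versus time curve to infinity, determined by log-linear trapezoidal estimation $AUC_{0-\tau} + C_{\tau}/k". The rate constant k "is the elimination rate constant defined as the negative slope following maximum concentration determined by least squares regression from terminal phase data". CL/F is dose over AUC0-∞, and Vd/F is dose over the product of k and AUC0-∞. The table is introduced as non-compartmental.
- **Text before the table.** The main route is a polyexponential fit. If there are too few post-peak points, a model-independent route applies. There AUC0-n covers the sampling period and AUC0-∞ = AUC0-n + Cp_n/λz, where Cp_n "represents the final plasma concentration predicted from the fitted apparent terminal elimination phase".

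Section 11.2, Research Visit 2, sets the first-dose sampling as "Study Design 1: 0.5, 0.75, 1, 1.5, 2, 3, 4, 6, 8, 10, 12, 16, 20, 24, 48, and 72 hours". Study Design 2 stops at 12 h. Figure 5 in Section 11.1 gives the same visit lengths (72 h and 12 h) and defines Study Design 1 as activity score below 1 or two reduced-function alleles.

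**The concern.** With τ = 24 h in Study Design 1, which is the natural reading of the table, the tail starts at 24 h. The area observed between 24 and 72 h is then replaced by C24/k, although children return at 48 and 72 h to be sampled. The text rule would start the tail at 72 h. Two analysts following the two descriptions would report different AUC0-∞, CL/F and Vd/F for the same child.

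Only Study Design 1 is affected. In Study Design 2, τ and the last sample coincide at 12 h. The steady-state table uses the same wording for AUC0-τ,ss, but Study Design 1 sampling does end at 24 h at Research Visits 3 and 4.

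At stake is how precisely exposure and clearance are measured in the slower metabolisers. These data feed the refinement of iGO-PK, a secondary objective, and Section 20.1 plots AUC0-∞ against pupillometry and eye-tracking data.

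**Working it through.** The plan states no half-life, extrapolated fraction or tolerance, so there is no figure of its own to reproduce. What follows rests on assumptions.

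**Inputs from the documents:** τ = 24 h and the formulas for AUC0-∞, CL/F and k (Section 20.1); 16 post-dose times to 72 h (Section 11.2).

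**Assumed:** one compartment, first-order absorption with ka = 1/h, half-life 4–30 h.

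**Step 1, share of AUC0-∞ beyond time T.** With k = ln 2 / half-life,

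share(T) = (ka·e^(−kT) − k·e^(−ka·T)) / (ka − k).

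At a half-life of 20 h, k = 0.0347/h and ka − k = 0.9653.
- T = 24: e^(−0.832) = 0.435, and 0.435/0.9653 = 45.1%.
- T = 72: e^(−2.495) = 0.0825, and 0.0825/0.9653 = 8.5%.

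**Step 2, effect on CL/F.** 4,000 profiles were simulated per half-life at the Study Design 1 times, with an assumed 15% log-normal concentration error, a linear-up/log-down trapezoid and observed concentrations at the start of the tail. Three rules were compared:
- A: tail from 24 h, k from the 12–24 h samples only
- B: tail from 24 h, k from the 16–72 h samples
- C: tail from 72 h, k from the 16–72 h samples

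The SD of the CL/F error is the interquartile range divided by 1.349. Under A, profiles with a non-positive fitted k were dropped.

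| Half-life (h) | Tail from 24 h | Tail from 72 h | SD, A | SD, B | SD, C |
|---|---|---|---|---|---|
| 4 | 1.9% | 0.0% | 4.7% | 4.7% | 4.7% |
| 8 | 13.7% | 0.2% | 5.7% | 4.5% | 4.3% |
| 12 | 26.5% | 1.7% | 11.3% | 5.4% | 4.6% |
| 16 | 37.0% | 4.6% | 18.0% | 6.2% | 4.7% |
| 20 | 45.1% | 8.5% | 25.8% | 7.3% | 5.0% |
| 24 | 51.5% | 12.9% | 34.4% | 8.6% | 5.8% |
| 30 | 58.8% | 19.4% | 43.6% | 10.2% | 7.5% |

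Median bias in CL/F is below 1% under B and C, and at most about 4% under A (at 30 h).

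**Step 3, noise-free check.** With the true k and no error, the 24 h and 72 h rules give the same AUC0-∞ (0.999 of the true value at 20 h for both). Under a log-linear decline, therefore, the choice of starting point costs precision and does not introduce bias.

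**The case against.** The strongest reply is that the plan already contains the right rule. The text before the table integrates over the whole sampling period and starts the tail at the final concentration, and its main route is a polyexponential fit to all the data. This stands in part: the plan is not settled on stopping at 24 h. It does not remove the conflict. The sampling-period rule sits in the fallback for too few post-peak points, while the table is introduced separately as what will be derived by non-compartmental analysis.

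The second reply is that a 45% tail is not a 45% error. That stands. The table takes k from terminal-phase data with no 24 h cap, so rule B is closer to what is written than rule A. If the tail also started from the fitted concentration at 24 h, as the text does for its own final concentration, the loss nearly disappears: the CL/F error SD at 20 h is again about 5%.

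The third reply is that Study Design 1 includes intermediate metabolisers, whose half-lives may be shorter. At 4–8 h the two rules hardly differ.

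A reader might also point to the poor-metaboliser model in Section 5.1, with its "first order clearance, and a secondary peaking component", as evidence that extrapolating from 24 h is biased. The documents give no timing for that peak, and the simulation above does not include it. It is a reason to prefer observed area, but it does not demonstrate bias.

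**Conclusion.** The inconsistency is real. For Study Design 1, the table's AUC0-∞, and with it CL/F and Vd/F, omits observed area that the text's rule would use. How much of AUC0-∞ is then extrapolated depends on a half-life that the documents do not state: about 2–14% at 4–8 h and 45–52% at 20–24 h, against 9–13% from 72 h at 20–24 h. The consequence is modest extra imprecision, about 7% against 5% SD in CL/F at 20 h, with little bias if the decline is log-linear and k uses the late samples. These figures assume one compartment, ka of 1/h and 15% concentration error.

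A reader might infer that clearance in slow metabolisers would be badly misestimated. That needs k to be confined to data up to 24 h (SD about 26% at 20 h), and no section says so. Nor do the documents say that the 72 h visit exists to measure CL/F, or plan a CL/F comparison among the Study Design 1 genotype groups. The primary objectives are pharmacodynamic and clinical, and dosing targets Cmax,ss. The point is worth correcting because the plan leaves the rule open and the better choice costs nothing.

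**What to change.** In the single-dose table of Section 20.1:

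1. Define AUC0-∞ = AUC0-last + C_last/k, where last is the final quantifiable sample (up to 72 h in Study Design 1, 12 h in Study Design 2), and derive CL/F and Vd/F from it.
2. Make the text and the table agree on whether C_last is observed or predicted, and say whether the polyexponential or the non-compartmental values take precedence.
3. State that k uses the 48 and 72 h samples where quantifiable.
4. Keep AUC0-12 or AUC0-24 as a separately named partial area; AUC0-12 is available in both designs.
5. Report the percentage extrapolated for each child. A flag at 20% is an optional benchmark and is not taken from the documents.

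The cost is one changed table row and a few sentences of text. All the samples are already scheduled, so no visit or procedure changes.

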Table is edited from (Caudle et al., 2020).

Functional scores for the reference: \*1 = 1, \*2 = 1, \*3 = 0, \*4 = 0, \*5 = 0, \*6 = 0, \*10 = 0.25, \*41 = 0.5.

Additionally, data generated from studies conducted at Children's Mercy Hospital has suggested that changes in study design assignment are warranted, particularly for children with an activity score of 1, which could be a result of having two reduced function CYP2D6 alleles (0.5/0.5) or one functional copy and one non-functional copy of CYP2D6 (1/0). The studies mentioned above are: Ped Develop Pharm U54 (IRB# 16010069) and this study, ATX-PBPK-PD-Clinical Outcomes (U54) (IRB# 16100728). Initial analysis suggests that 0.5/0.5 children have higher ATX exposure compared to 1/0 children, suggesting slower ATX apparent oral clearance. Additionally, 1/0 children more closely resembled children with two fully functional copies of CYP2D6 in their pharmacokinetics.

This preliminary data generated from previous ATX studies and the revised CPIC guidelines have prompted the study team to revise study design assignment. Therefore, to ensure that each participant's ATX pharmacokinetics are accurately characterized, all children with an activity < 1 and those who have a two reduced function alleles will be assigned to Study Design 1. All other participants will be initially assigned to Study Design 2.

Additional genotype testing may be conducted if the participant's pharmacokinetic profile and genotype are inconsistent with one another. The additional genotype testing, if needed, will be documented on the provided CRF.

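### Steady-state CL/F and Vd/F are divided by AUC to infinity, and the steady-state AUC window follows study design instead of dosing interval

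*Combined protocol and SAP*

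**What the plan says.** Section 20.1 (Pharmacokinetics) has two parameter tables, one for the single dose and one for chronic dosing. The second opens: "The following PK parameters will be derived by non-compartmental analysis from plasma concentration data following chronic dosing to steady-state of study drug". Its CL/F_ss row reads "Oral clearance determined by quotient dose" over AUC0-∞. Its Vd/F_ss row reads "Terminal phase volume of distribution determined by Dose" over k times AUC0-∞. Both rows match the single-dose table word for word.

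The steady-state table has no AUC0-∞ row. It lists AUC0-τ,ss but does not use it for clearance, and runs it "to the 12 or 24 hour time point (depending on CYP2D6 AS designated study design").

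The text above the tables describes "extrapolation of the AUC to infinity" as the AUC over the sampling period plus the last predicted concentration divided by λz. It gives no correction for drug carried over from earlier doses.

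Other relevant places:

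- Section 5.1 (iGO-PK Model) describes non-poor metabolisers by a "two-compartment model with first order absorption and first order clearance" and poor metabolisers by a "one compartment model with first order absorption, first order clearance, and a secondary peaking component".
- Section 11.1 treats once-daily dosing as usual, with some Design 2 participants moved to twice daily. Design 3 is for twice-daily dosing that is not every 12 h.
- Section 11.2 samples Design 1 to 24 h and Design 2 to 12 h at Research Visits 3 and 4. Design 3 is sampled to 16 h after the second dose. A pre-dose sample is taken in every design.

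**The concern.** Under first-order kinetics at steady state, the dose given in one interval equals CL/F times the AUC over that interval. AUC0-∞ from the same profile adds the residue of all earlier doses, so dose/AUC0-∞ is too small, and Vd/F_ss falls by the same factor. The slower the elimination, the more drug is carried over, so the error is largest in slow metabolisers.

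The window is a second, separate problem. A 12 h AUC is a full interval for 12-hourly dosing but half of one for once-daily dosing. The same label, AUC0-τ,ss, would then mean different things in Designs 1 and 2.

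At stake are the reported steady-state parameters and any comparison of them across CYP2D6 groups or designs. Section 5.1 shows the team making such a clearance comparison ("suggesting slower ATX apparent oral clearance"), without saying whether it came from single-dose or steady-state data.

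**Working it through.** The plan gives no figure to reproduce.

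**Inputs from the documents.** The formulas and AUC limits are those of section 20.1. Sampling times are those of section 11.2. The dosing interval is 24 h when once daily and 12 h when every 12 h. First-order kinetics come from section 5.1.

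**Assumptions.** Half-life 2–24 h; absorption rate ka 1.5 per hour; doses superposed to steady state; linear-up/log-down trapezoid at the protocol times; k from the last four samples (last three in Design 3).

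**Closed form, ignoring absorption time**

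True CL/F = dose/AUC0-τ,ss. The table gives dose/(AUC0-τ,ss + Cτ/k). The ratio of reported to true is 1 − e^(−kτ) = 1 − 2^(−τ/t½). For τ = 24 h:

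- t½ 6 h: 1 − 2^(−4) = 0.938
- t½ 12 h: 1 − 2^(−2) = 0.750
- t½ 24 h: 1 − 2^(−1) = 0.500

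**Simulated oral profiles, error in CL/F_ss and Vd/F_ss**

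| Setting | Half-life: error |
|---|---|
| Design 1, once daily | 6 h: −6.4%; 8 h: −13.0%; 12 h: −25.6%; 16 h: −36.0%; 20 h: −44.1%; 24 h: −50.5% |
| Design 2, once daily | 2 h: +1.1%; 3 h: +0.3%; 5 h: −3.5%; 6 h: −6.4%; 8 h: −13.0% |
| Design 2, every 12 h | 2 h: −0.9%; 3 h: −6.7%; 5 h: −20.2%; 6 h: −26.3% |

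Dose/AUC0-24 in Design 1 is within 0.4% of the truth.

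Sensitivity checks:

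- Changing ka to 0.8 or 3.0 per hour moves the errors by at most about 2 percentage points.
- A secondary peak in Design 1 (10–30% of the dose, 4–8 h late) gives −26 to −29% at 12 h and −51 to −52% at 24 h.
- Two-compartment profiles in once-daily Design 2 give +4% to −14%.

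**Effect on a comparison of metaboliser groups, equal volumes assumed**

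- 6 h v 24 h: true ratio 24/6 = 4.0; reported 4.0 × 0.936/0.495 = 7.6.
- 6 h v 12 h: true ratio 12/6 = 2.0; reported 2.0 × 0.936/0.744 = 2.5.

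**Window in once-daily Design 2**

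| Half-life | 2 h | 3 h | 5 h | 6 h | 8 h |
|---|---|---|---|---|---|
| AUC0-12 as a share of AUC0-24 | 0.969 | 0.923 | 0.820 | 0.780 | 0.720 |
| CL/F_ss error if only the formula is corrected | +3.2% | +8.3% | +21.9% | +28.3% | +38.9% |

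The second row is 1/share − 1; for example, 1/0.720 = 1.389. Two-compartment shares are 0.71–0.92.

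**The case against.** **AUC0-∞ could mean the Research Visit 2 value.** It is defined only in the single-dose table and carries no steady-state subscript. Paired with the Visit 2 dose it is unbiased under linear kinetics, and the percentages above would not apply. But it would only repeat single-dose CL/F under a steady-state label. Paired with a later titrated dose it would be wrong in proportion to the dose change: moving from the 400 to the 800 ng/mL target is a factor of 800/400 = 2 under linear kinetics. Either reading needs correction.

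**Curve fitting comes first in section 20.1, and a fit that included earlier doses would be free of this bias.** That is true of such a fit. But the section mentions no multiple-dose terms, and the lead-in assigns these rows to non-compartmental analysis.

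**No planned analysis is shown to be harmed.** This largely stands. The hypotheses in section 2.2 do not use CL/F_ss or Vd/F_ss, and the documents do not say that iGO-PK refinement uses them. Exposure is targeted on Cmax, and single-dose CL/F remains available for CYP2D6 comparisons. No AUC0-τ,ss comparison across designs is specified.

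**The 7.6-fold example is at the top of the assumed range.** It is, which is why the 2.5-fold case is shown beside it. Design 1 also includes participants who are not poor metabolisers.

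**Design 3 may inherit the 12 h limit, since its participants come from Design 2.** That is possible, but 12 h would not be a dosing interval for them.

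**Conclusion.** The concern holds as a minor error of definition. Followed as written, section 20.1 understates CL/F_ss and Vd/F_ss by 6–50% in once-daily Design 1 (half-life 6–24 h) and by 1–26% on 12-hourly dosing in Design 2 (2–6 h). In once-daily Design 2 the effect is small, from +1% to −13% (2–8 h). AUC0-τ,ss in once-daily Design 2 is 3–28% below the 24 h value at the same daily exposure. These sizes rest on assumed half-lives, linear kinetics and AUC0-∞ being taken from the steady-state profile.

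Not affected: Cmax,ss, the single-dose parameters, the 0–24 h window in once-daily Design 1, the 0–12 h window for 12-hourly dosing in Design 2, and AUC compared between visits within one design over the same window.

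**What to change.** Amend the steady-state table in section 20.1:

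- Define τ as the participant's actual dosing interval. Set CL/F_ss = dose per interval/AUC0-τ,ss and Vd/F_ss = dose per interval/(k·AUC0-τ,ss).
- **Once-daily Design 2:** complete 12–24 h using that visit's pre-dose sample as the 24 h value, where the previous dose time is recorded and close to 24 h earlier (for example 22–26 h). Otherwise extrapolate log-linearly with k. Flag which was used.
- **12-hourly dosing in Design 2:** keep 0–12 h.
- **Design 3:** use total daily dose over the 0–24 h AUC from the first dose, extrapolating with k where sampling stops short of 24 h. The 22–26 h pre-dose condition will generally not be met here, because the previous dose is the preceding day's second dose. The k route is accurate to about 1% for gaps of 4–10 h between doses.
- Change formula and window together, for the reason shown in the second table.
- Where an AUC is used to show change in exposure between visits, use the same window at Research Visit 2 and at Visits 3 and 4, so that real accumulation is kept.

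The cost is an edit to definitions, with no extra blood draws. Revision 17.0 added a prior-day time to the case report forms; this appears to be the dose time but is not stated to be, and earlier participants may lack it. In the simulations, pre-dose completion is within about 1% when the previous dose was 24 h earlier and about 4% at 22 or 26 h. Extrapolation with k is within about 1% and 2.5% respectively in one compartment, but about 1–5% low under two compartments.
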